4.10.1.5 Examination of Subgroups

The intent of the subgroup analyses is to demonstrate the consistency of response of a treatment across a wide range of the intended treated population. The subgroups of interest are defined below:

- Baseline Smoking status [current smoker, former smoker]
- Age group [<65 years,  $\geq 65$  years]
- Sex [Male, Female]
- Reversibility to ipratropium [yes, no]
- Concomitant ICS use [yes, no]
- Concomitant LABA use [yes, no]
- Baseline post bronchodilator % predicted FEV1[50% to <80%, 30% to <50%, <30%] (GOLD airflow categories [2, 3, 4])
- GOLD categories [A, B, C, D]
- Ethnicity [North East Asian, South East Asian], provided by external data vendor of spirometry assessments.

North East Asian defined as China north of the Huaihe River and Qinling Mountains. South East Asian defined as China south of the Huaihe River and Qinling Mountains.

#### 4.10.1.6 Interim Analyses

Not Applicable

#### 4.10.2 Primary Efficacy Variable – CBL Trough FEV1 on Day 85

The primary efficacy variable is the change from baseline trough  $FEV_1$  on Day 85.

- Baseline FEV1 is defined as the average of the -45 and -15 minute measurements prior to dosing of study medication on Day 1 (Visit 3).
- Trough FEV1 measurements will be the pre-dose FEV1 measures on Days 29, 57 and 85 calculated as the average of the -45 and -15 minute measurements prior to dosing of study medication.
- If a public health emergency prevents FEV1 data from being measured at site then information on the reasons for the missing assessments will be recorded in the CRF

If either of the two pre-dose  $FEV_1$  measures is missing, the baseline/trough will be set to the value of the remaining non-missing measure. If both pre-dose values are missing then the baseline/trough will be set to missing.

If no baseline can be calculated for the subject, then the change from baseline values will be recorded as missing. Change in  $FEV_1$  is calculated as the Trough  $FEV_1$  – Baseline  $FEV_1$  difference such that a positive change indicates improvement.

The absolute values and the change from baseline trough FEV1 will be summarized by treatment group and visit using summary statistics for continuous data.

## 4.10.2.1 Primary Analysis

The analysis of the primary endpoint will be based on a mixed model repeated measures (MMRM) analysis including changes from baseline trough FEV1 measurements on Days 29, 57 and 85 as the dependent variable. The model will include independent fixed-effect terms for concomitant LABA use, reversibility to ipratropium, smoking status, age, sex, treatment and baseline FEV1 as a covariate. A time effect (visit) and its interaction terms with treatment and baseline FEV1 will be included. The variance estimation will be based on an unstructured covariance matrix. The Kenward-Roger method for approximating the denominator degrees of freedom will be used.

The primary analysis of the primary efficacy endpoint will be based on the Full Analysis Set (FAS) population and includes all randomized subjects who received at least one dose of study drug and have at least one recorded post-baseline FEV1 assessment. Available data for a subject prior to discontinuing study treatment will be used in the MMRM analysis. Missing data is assumed as missing at random (MAR). The robustness of the conclusions to this assumption will be assessed with a missing data sensitivity analysis.

The difference between revefenacin and placebo on Day 85 will be estimated from the least squares means (LS means) along with the 95% confidence interval (CI) and associated 2-sided p-values. As a supportive analysis, the primary efficacy analysis will be performed using the Per-Protocol (PP) Analysis Set.

#### 4.10.2.2 Primary Endpoint Sensitivity Analysis

Sensitivity analyses using missing data imputation methods are included to assess the robustness of the primary estimate with regard to missing data.

#### Multiple Imputation (MI) Tipping Point Analysis

A sensitivity analysis using a two-dimensional tipping point imputation method will be applied to the MMRM analysis (FAS population) to assess the robustness of the conclusions to the assumption that missing data is MAR. In the tipping point analysis a succession of delta adjustments via multiple imputation methods will be used to impute the missing revefenacin and placebo trough FEV1 values at each timepoint. The tipping point is denoted as the mean trough FEV1 value that would have to be imputed to overturn a statistically significant result. Clinical judgement will be applied to the plausibility of the tipping point. The detail of this imputation method and example SAS code is given in Appendix.

## Single Imputation Last-Observation-Carried-Forward (LOCF) Approach

The LOCF method described in Section 4.10.1.3 will be used for subjects with missing trough  $FEV_1$  data on Day 85. Change from baseline trough  $FEV_1$  at Day 85 will be analyzed

using an analysis of covariance (ANCOVA) using the FAS population. The model will include treatment, and concomitant LABA use, bronchodilator reversibility to ipratropium, smoking status, age, sex, baseline  $FEV_1$  as covariates.

Least squares means for Day 85 will be derived for both treatment groups. The difference between revefenacin and placebo on Day 85 will be estimated from the LS means along with the 95% CI and associated 2-sided p-values.

4.10.2.3 Primary Endpoint Subgroup Analysis

An assessment of whether the effect of treatment on the primary endpoint is modified by each Subgroup of Interest (see Section 4.10.1.5) will be made by fitting separate MMRM models, identical to the model described for the primary analysis, but including additional terms for the subgroup and treatment by subgroup interaction.

Based on this MMRM model, LS means and standard errors for treatment within subgroup and LS means and two-sided 95% CIs for treatment differences within subgroup will be provided.

LS mean differences between groups (calculated as Revefenacin – placebo) and associated CI will also be presented by Forest Plot for each subgroup and categories within the subgroup.

The number of subjects in each treatment group and subgroup will be reviewed. Subgroups may need to be regrouped or excluded from analyses where insufficient numbers exist. The reasons why subgroup analyses are not performed will be documented.

#### 4.10.3 Secondary Efficacy Variables

In all the secondary efficacy analyses the FAS population will be used and missing data will not be imputed and will be assumed to be missing at random (MAR) unless otherwise stated. If a public health emergency prevents data from being measured or requires data to be assessed remotely via a virtual visit, then information on the reasons and the data impacted will be recorded in the CRF.

4.10.3.1 CBL Trough FEV1 and FVC

The changes from baseline trough  $FEV_1$  on Days 29 and 57 will be estimated from the MMRM analysis used for the primary analysis of the primary endpoint.

The changes from baseline trough FVC on Days 29, 57 and 85 will be analyzed using the same MMRM analysis described for the primary analysis of the primary endpoint. The baseline  $FEV_1$  covariate will be replaced with the baseline trough FVC recorded on Day 1.

4.10.3.2 CBL to Peak  $FEV_1$  (0-2h) on Days 1 and 85

Lung function assessments will be made after study treatments (5, 15, and 30 minutes, and 1, 1.5, and 2 hours) on Day 1 and Day 85. Peak  $FEV_1$  is defined as the highest post-dose  $FEV_1$  value within 2 hours after the dosing on Day 1.

Peak  $FEV_1$  on Day 1 and Day 85 will be summarized by treatment group for the actual value and for the change from baseline on Day 1.

An ANCOVA model will be used to assess the difference between treatment groups for the change from baseline to Peak  $FEV_1$  after the first dose on Day 1. The ANCOVA model will include treatment, and concomitant LABA use, reversibility to ipratropium, smoking status, age, sex, baseline  $FEV_1$  as covariates.

The difference between revefenacin and placebo on Day 1 will be estimated from the LS means along with the 95% CI and associated 2-sided p-values.

A separate analysis will be performed for Peak FEV1 on Day 85 using the same ANCOVA model.

4.10.3.3 CBL in Weighted Mean FEV1 (0-2h) on Days 1 and 85

The area under the curve (AUC) [0 to 2] hours will be calculated using the trapezoidal rule, including observed data points from the pre-dose (0 hour) through to the 2 hour observation. For all observations the nominal time of the observation should be used. For the calculation of AUC, the first (0 hour), last (2 hour) and at least one time point between first and last must be available. Otherwise, the AUC is set to missing. The Baseline FEV1 on Day 1 and Trough FEV1 on Day 85 will be used as the 0 hour data point to calculate the AUC for Day 1 and Day 85, respectively.

The weighted mean (WM)  $FEV_1$  is derived from dividing AUC by the total time (nominally 2 hours).

An ANCOVA model will be used to assess the difference between treatment groups for change from baseline in WM FEV1 after the first dose on Day 1. The ANCOVA model will include treatment, and concomitant LABA use, reversibility to ipratropium, smoking status, age, sex, baseline  $FEV_1$  as covariates.

The difference between revefenacin and placebo on Day 1 will be estimated from the LSmeans along with the 95% CI and associated 2-sided p-values.

A separate analysis will be performed for WM FEV1 on Day 85.

4.10.3.4 CBL SGRQ Total Score on Day 85

The SGRQ total score and 3 component scores, including symptoms, activity, and impacts, will be derived. Baseline SGRQ endpoints will be those recorded on Day 1 (Visit 3). The baseline and Day 85 absolute values and the change from baseline in SGRQ total score and 3 component scores will be summarized by treatment group (continuous data).

An ANCOVA model will be used to assess the difference between treatment groups for change from baseline SGRQ total score on Day 85. The ANCOVA model will include treatment, and concomitant LABA use, reversibility to ipratropium, smoking status, age, sex, baseline SGRQ total score as covariates. For subjects who discontinue study treatment, the data from the SGRQ completed at the Early Termination (ET) visit will be carried forward in the analyses.

The difference between revefenacin and placebo on Day 85 will be estimated from the LSmeans along with the 95% CI and associated 2-sided p-values.

The three SGRQ components will be similarly analyzed.

4.10.3.5 Number (%) of SGRQ Responders (Total Score ≥4 Units) on Day 85

A decrease from baseline of  $\geq$ 4 units in SGRQ total score is considered clinically meaningful and will be defined as a responder.

The number and percentage of responders on Day 85 in each treatment group will be summarized. A comparison between revefenacin and placebo will be evaluated with the odds ratio (OR) and corresponding 95% confidence interval from a logistic regression model. The model will include fixed-effect terms for concomitant LABA use, reversibility to ipratropium, smoking status, age, sex, treatment and baseline SGRQ total score as a covariate.

For subjects who discontinue study treatment, the SGRQ completed at the Early Termination (ET) visit will be carried forward and used to derive a responder.

4.10.3.6 TDI Focal Score on Days 29, 57 and 85

The BDI and TDI focal scores and associated components will be listed and summarized by treatment and visit using summary statistics. Baseline BDI scores will be recorded on Day 1 (Visit 3). The TDI questionnaire represents changes from baseline and will be recorded on Days 29, 57 and 85.

The BDI/TDI scores include three components: functional impairment, magnitude of task, and magnitude of effort. For BDI scores, each domain can be rated from Grade 0 (very severe) to 4 (no impairment). For TDI scores, each domain can be rated from Grade -3 (major deterioration) to + 3 (major improvement). The focal score is the sum of the three components (ie BDI ranges from 0 to 12 and TDI ranges from -9 to +9).

The TDI focal score will be analyzed using the same MMRM analysis described for the primary analysis of the primary endpoint. The baseline  $FEV_1$  covariate will be replaced with the BDI focal score. Estimates for TDI on Days 29, 57 and 85 will be derived from the model.

The difference between revefenacin and placebo on Days 29, 57 and 85 will be estimated from the LSmeans along with the 95% CI and associated 2-sided p-values.

The three TDI components will be analyzed in a similar way.

Details of BDI/TDI are further described in Section 6.6.

4.10.3.7 Number (%) of TDI Responders (Focal Score ≥1) on Days 29, 57 and 85

A TDI focal score of  $\geq 1$  unit is considered clinically meaningful and will be defined as a responder.

The number and percentage of responders on Days 29, 57 and 85 in each treatment group will be summarized. A comparison between revefenacin and placebo will be evaluated with the odds ratio (OR) and corresponding 95% confidence interval from a logistic regression model

including the proportion of responders at each visit (Days 29, 57 and 85) as the dependent variable. The MMRM logistic (binomial distribution with logit link function) model will include the same independent fixed-effect terms as for the primary analysis of the primary endpoint. The baseline FEV1 covariate will be replaced with the BDI focal score as a covariate. Estimates for the proportion of TDI responders on Days 29, 57 and 85 will be derived from the model.

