### 7.4.1 Spirometry

#### 7.4.1.1 Trough FEV1 on Days 29 and 57

The changes from baseline trough FEV1 on Days 29 and 57 will be estimated from the MMRM analysis used for the primary analysis of the primary endpoint.

#### 7.4.1.2 Trough FVC on Days 29, 57 and 85

The changes from baseline trough FVC on Days 29, 57 and 85 will be analyzed using the same MMRM analysis described for the primary analysis of the primary endpoint. The baseline FEV1 covariate will be replaced with the baseline trough FVC recorded on Day 1.

#### 7.4.1.3 Peak FEV1 (0-2h) on Day 1 and Day 85

Lung function assessments will be made after study treatments (5, 15, and 30 minutes, and 1, 1.5, and 2 hours) on Days 1 and 85.

Analysis of Covariance (ANCOVA) model will be used to assess the difference between treatment groups for change from baseline Peak FEV1 after the first dose on Day 1. The ANCOVA model will include fixed-effect terms for concomitant LABA use, reversibility to ipratropium, smoking status, age, sex, treatment and baseline FEV1 as a covariate.

The difference between refefenacin and placebo on Day 1 will be estimated from the LSmeans along with the 95% CI and associated 2-sided p-values.

A separate analysis will be performed for Peak FEV1 on Day 85 using the same ANCOVA model.

#### 7.4.1.4 Weighted Mean FEV1 (0-2h) on Day 1 and Day 85

Lung function assessments will be made after study treatments (5, 15, and 30 minutes, and 1, 1.5, and 2 hours) on Days 1 and 85.

The area under the curve (AUC), (0 to 2h) will be calculated using the trapezoidal rule including observed data points from pre-dose (0 hours) through to the 2 hour observation. For all observations the nominal time of the observation should be used. For the calculation of AUC, the first, last and at least one time point between first and last must be available. Otherwise, the AUC is set to missing.

The weighted mean (WM) FEV1 is derived by dividing AUC by the total time (nominally 2 hours).

An ANCOVA model will be used to assess the difference between treatment groups for WM FEV1 on Day 1 and Day 85 in separate models. Each ANCOVA model will include fixed-effect terms for concomitant LABA use, reversibility to ipratropium, smoking status, age, sex, treatment and baseline FEV1 as a covariate.

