## 4.12 Determination of Sample Size

The objective of this study is to confirm the efficacy of 12 weeks treatment with revefenacin 175 mcg compared with placebo administered once-daily in subjects with moderate to very severe COPD. The primary endpoint is change from baseline trough  $FEV_1$  at Day 85. The comparison of interest for the primary analysis is revefenacin 175 mcg versus placebo.

For each test on each efficacy endpoint, the null hypothesis is that there is no difference between the treatment groups.

H0: 
$$\mu_{rev} - \mu_{pbo} = 0$$

The alternative hypothesis is that there is a difference.

 $H_1: \ \mu_{rev} - \mu_{pbo} \neq 0$ 

The estimate for the difference in mean change from baseline trough  $FEV_1$  at Day 85 and the common standard deviation are based on the sample size assumptions for the revefenacin US pivotal studies (0126 and 0127) in a Western population and the GLOW7 study - a similarly designed study in a predominantly Chinese population (Wang et al., 2015).

A sample size of 256 evaluable subjects (128:128; a 1:1 ratio of revefenacin to placebo) is required to provide at least 90% power to detect a difference between revefenacin and placebo of 100 mL in the analysis of the change from baseline trough FEV1 at Day 85 assuming a standard deviation of 245 mL and a two-sided 5% significance level.

To allow for a 20% dropout rate, approximately 320 subjects in total will be randomized. In the event of a public health emergency such as COVID-19, the Sponsor may consider increasing enrollment to overcome any additional loss of information for the primary endpoint due to the inability of subjects to attend for scheduled clinic visits. The maximum number of subjects to be randomized under such circumstances will be limited to 428 (an additional 20% increase in enrollment).

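### Day 85 Peak and weighted-mean FEV1 rest on single-visit ANCOVAs that in effect use only subjects with Visit 6 serial spirometry; a Day 1 plus Day 85 repeated-measures model would need a weaker missing-data assumption and be slightly more precise

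*SAP*

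**What the plan says.** For secondary endpoints, SAP 4.10.3 states that "missing data will not be imputed and will be assumed to be missing at random (MAR) unless otherwise stated". For Peak FEV1, SAP 4.10.3.2 specifies an ANCOVA on Day 1 and a separate one "on Day 85 using the same ANCOVA model". Its covariates are treatment, LABA use, reversibility, smoking status, age, sex and baseline FEV1. SAP 4.10.3.3 also gives weighted-mean FEV1 a separate Day 85 analysis. Protocol 7.4.1.4 describes the weighted-mean analyses "on Day 1 and Day 85 in separate models", and SAP Table 6 lists ANCOVA for both endpoints.

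Other provisions decide who enters the Day 85 models:

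- Serial post-dose spirometry is done at Visits 3 and 6 only (SAP 3.1.2.2).
- The early termination visit has two sessions that match the pre-dose ones and no post-dose series (Protocol 6.2.5). Mapping that visit to a scheduled day (SAP 4.3.3) can supply a trough value, but not a Peak or a weighted mean.
- Imputation-based sensitivity analyses cover only the primary endpoint (SAP 4.10.1.3).
- SGRQ carries the early termination value forward (SAP 4.10.3.4 and 4.10.3.5). Peak and weighted mean have no counterpart.
- Trough FEV1, FVC and TDI are analysed by MMRM, which keeps the partial data of subjects who stop early.

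**The concern.** The Day 85 analyses are labelled FAS. Subjects who stop early are normally in the FAS, because a Day 1 post-dose FEV1 is a post-baseline efficacy assessment. Yet they contribute nothing to the Day 85 Peak or weighted-mean contrast. The same holds for a subject whose Visit 6 is replaced by a telephone visit (Protocol 6.6).

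A single-visit ANCOVA cannot condition on anything observed after randomization. If poor early responders leave more often, and this differs by arm, those who remain are a selected group and the Day 85 difference shifts. Dropout related to outcome is plausible here, because a moderate or severe exacerbation requires termination of study drug (Protocol 4.2.4). The Day 1 post-dose measurements could correct part of this and recover some precision, but the models do not use them.

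**Working it through.** **Inputs from the documents.** The SD is 245 mL, two-sided alpha is 5%, 128 per arm are evaluable, and dropout is 20% (SAP 4.12). The SD is for trough FEV1 and stands in here for Peak and weighted mean, for which the plan gives neither an SD nor an effect.

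**Inputs that are assumptions.** The documents do not give the correlation ρ between Day 1 and Day 85 response given covariates, the dependence of dropout on earlier response, dropout by arm, or the true Day 85 effect.

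**1. The plan's own figure.** The plan states that its sample size "is required to provide at least 90% power to detect a difference between revefenacin and placebo of 100 mL", "assuming a standard deviation of 245 mL".

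- n per arm = 2 × (1.960 + 1.282)² × 245² / 100² ≈ 126.1, rounded up to 127; the plan uses 128.
- SE at 128 per arm = 245 × √(2/128) = 30.6 mL. Power = Φ(100/30.625 − 1.960) = 90.4%.
- 256 / 0.8 = 320 randomized.

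The sample size reproduces.

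**2. Precision.** If a fraction d lacks Day 85 data and dropout is non-informative, the SE of the joint model relative to the ANCOVA is √(1 − dρ²). With d = 0.20:

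| ρ | SE ratio | Joint-model SE | ANCOVA SE |
|---|---|---|---|
| 0.5 | √(1 − 0.2 × 0.25) = 0.975 | 29.9 mL | 30.6 mL |
| 0.7 | √(1 − 0.2 × 0.49) = 0.950 | 29.1 mL | 30.6 mL |

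The joint-model SE is 2.5% to 5.0% smaller. Nominal power for a 100 mL difference would rise from 90.4% to 91.8% and 93.0%. With d = 0.40 the ratios are √0.90 = 0.949 and √0.804 = 0.897.

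**3. How bias arises.** With equal SDs and a linear relation between the two days, the bias of the completer difference is ρ times a difference between arms. That difference is in how far the mean Day 1 response of completers lies above that of all subjects in the arm. If this shift is the same in both arms, it cancels. The joint model estimates the term and removes it.

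**4. Simulation with arm-specific dropout.** Settings: 160 per arm, SD 245 mL, true effect 100 mL on both days, 20,000 trials per setting. Where dropout depends on Day 1, the log-odds of dropping out rise by 0.7 per SD lower Day 1 response relative to the subject's own arm.

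| Dropout depends on Day 1 response | Dropout, placebo / revefenacin | ANCOVA mean, ρ = 0.5 | ANCOVA mean, ρ = 0.7 |
|---|---|---|---|
| No | 20% / 20% | 100.3 | 100.3 |
| Equally in both arms | 20% / 20% | 100.0 | 100.2 |
| Equally in both arms | 25% / 15% | 92.4 | 89.6 |
| Placebo only | 25% / 15% | 80.2 | 72.6 |

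The joint model averaged 99.9 to 100.3 mL in all of these settings.

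**5. Simulation with one dropout rule for both arms.** Dropout depends on the actual Day 1 response, the effect is 150 mL on both days, overall dropout is 20%, ρ is 0.5-0.7, and the log-odds are 0.4-1.0 per SD. Because the drug raises the Day 1 response, dropout becomes unequal without further assumption: 22-24% on placebo and 16-18% on revefenacin. ANCOVA bias was about -1 to -12 mL and joint-model bias was under 1 mL. With no dependence both were unbiased.

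**6. Dropout driven by response after Day 1.** An intermediate response was assumed to correlate 0.6 with Day 1 and 0.8 with Day 85. At log-odds 0.7 per SD, ANCOVA bias was -7 to -8 mL and the two-visit model kept about -4 mL. Across settings, about half to two-thirds of the bias remained.

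**The case against.** A reader might infer that these Day 85 estimates are biased, or that ANCOVA contradicts the SAP's missing-at-random statement. The documents support neither. A complete-case ANCOVA is valid when missingness depends only on treatment and the model covariates, which is itself a form of missing at random. Whether dropout departs from that, and in which direction, cannot be known from the plan. A reader might also take the lowest cell of the arm-specific table, or the -33 mL it reaches at ρ = 0.85 (66.8 against 100), as the likely size. That needs dependence in placebo only together with 25%/15% dropout, and both are assumptions.

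Further points against the concern:

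- **Small size.** 12 mL is 8% of 150 mL (12/150) and about 0.4 of an SE (12/30.6). In the settings tried the shift was toward no effect. This stands.
- **Incomplete remedy.** The near-zero bias of the joint model in step 5 follows from letting dropout depend on the variable that the model adds. Exacerbations during treatment occur after Day 1, and step 6 shows that only part of such bias is removed. This stands.
- **Day 1 analysis.** Day 1 data are nearly complete and nothing is wrong with that ANCOVA. This stands, and the fix leaves it alone.
- **Prespecification.** The protocol itself specifies separate ANCOVAs, a conventional choice for two visits 12 weeks apart. That makes the change a departure to document, but it is no reason to discard the Day 1 data.

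**Conclusion.** The point holds as a cheap improvement to secondary analyses; it does not show an error in the plan. Day 85 Peak and weighted-mean FEV1 are in effect completer analyses, need a narrower missing-data condition than the plan's MMRM endpoints, and have no sensitivity analysis.

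At the planned 20% dropout the possible bias is about 0 to -12 mL on an assumed 150 mL effect when dropout depends on Day 1 response. It is zero if dropout depends only on treatment and covariates, and about zero if the dependence and the dropout rates are alike in both arms. The opposite dropout pattern would reverse its sign. The SE is about 2-5% larger than necessary for ρ of 0.5-0.7.

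These sizes rest on the trough SD of 245 mL and on assumed correlations, effects and dropout patterns. In every setting tried, the two-visit model did at least as well as the ANCOVA, to within simulation error. The primary MMRM is unaffected.

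**What to change.** In SAP 4.10.3.2 and 4.10.3.3, and in Table 6, estimate the Day 85 contrast for each endpoint from a repeated-measures model with Day 1 and Day 85 as visits. Use the same covariates, treatment-by-visit and baseline-by-visit terms, an unstructured covariance matrix and Kenward-Roger degrees of freedom. Keep the Day 1 ANCOVAs as specified.

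The cost is SAP wording and reuse of the primary MMRM code with a two-level visit factor; no new data are needed. It is a small departure from Protocol 7.4.1.3 and 7.4.1.4, which Protocol section 7 allows the SAP to make, and it should be recorded in SAP 4.13. The text should also acknowledge that dropout driven by response after Day 1 is only partly addressed. Multiple imputation that uses the Day 1 post-dose values and the Day 29 and 57 troughs is an optional sensitivity analysis for that.
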